#### **5.1.2. Secondary Outcome Variable(s)**

Secondary outcome variables of the evaluation include:

Examining the BH-VPN's effect on additional patient outcomes as compared to usual care, such as

- a. CHS QCC defined 30-day readmission rate. This is a readmission rate among patients with an inpatient readmission to the same CHS facility as the index encounter. This measure applies to patients that have a hospital admission subsequent the ED encounter.
- b. The patient-centric defined 30-day readmission rate. This is a readmission rate among patients with an inpatient or observation readmission to any CHS facility. This measure applies to patients that have a hospital admission subsequent the ED encounter.
- c. 45-day post ED discharge utilization. Utilization is defined as an inpatient, observation, or ED encounter at a CHS facility.
- d. 90-day post ED discharge utilization. Utilization is defined as an inpatient, observation, or ED encounter at a CHS facility.

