## **OBJECTIVES**

### **1.1. Hypothesis**

Patients who have had a telepsychiatric consultation in the ED and also receive behavioral health care navigation will have a lower ED to inpatient conversion than patients who receive usual care.

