The Hospital Improvement Innovation Network (HIIN) is a nationwide effort to reduce preventable hospital acquired conditions and hospital readmissions. Part of the HIIN effort surrounding behavioral health patients, includes identifying packages or key components most effective at preventing psychiatric admission and exploring ways to efficiently apply effective strategies. As a complement to the telepsychiatry program, a partnership has been formed with HIIN to develop a patient navigator program to provide short-term follow up to patients who are evaluated by telepsychiatry and potentially eligible for discharge home. The patient navigator will connect with the patient virtually prior to discharge from the ED and assist the patient in obtaining services and overcoming any barriers for 45 days post ED discharge.

By providing this wrap-around service to complement Carolinas HealthCare System's telepsychiatry program, we expect to decrease the number of patients admitted for inpatient psychiatric treatment and increase the number of discharges from the ED by providing another layer of service to our providers and patients. Additionally, we aim to decrease hospital inpatient admissions and increase after-care compliance with medications and appointments through short-term follow up. In one study regarding inpatient psychiatric care, it was found that patients who did not comply with at least one outpatient appointment after discharge were two times more likely to be readmitted than those who kept at least one appointment after discharge.

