## **4.4. Evaluable Population**

Patients included in the evaluable population for this project, will have their data inform the final outcomes assessment. All patients who meet the inclusion criteria and have a completed telepsychiatric consult will be assessed. Evaluation will be by intent to treat. All patients in the both arms will be assessed for the primary outcome. Patients admitted directly from the ED or have neurocognitive disabilities from the intervention arm will not receive services from the BH-VPN. Patients in either arm have the following potential disposition: (admission to the hospital for medical reasons, admission to a behavioral health facility by voluntary or involuntary commitment, discharge from the ED, or death).

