## **5. OVERALL DESIGN**

### **5.1. Outcome Variables**

#### **5.1.1. Primary Outcome Variable**

The primary outcome variable is ED to inpatient or observation conversion. This is a patient that presents to either of the two CHS ED sites and then within 5 days of their ED discharge are admitted for any reason to a CHS facility as an inpatient or observation patient. In the electronic medical record, 2 hospital encounters are shown, the ED encounter and the inpatient\observation hospital encounter. Based on data from 2016 at CHS, most patients discharged from the ED who convert to an admission do so within 2 days of their ED discharge. Five days were chosen to maximize the conversions attributed to the ED encounter.

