## 6.2. Statistical analysis

All analyses will follow intention to treat such that patients will be analyzed based on the allocated intervention on the day of their ED visit (BH-VPN or treatment as usual). We will compare the two groups on age, sex, suicide ideation, and neurocognitive disorders to assess for balance, which is inferred with randomization.

The primary outcome, inpatient admission  $\leq 5$  days, will be compared between the two groups of patients using a chi-square test. We will explore differences by site by conducting stratified analysis by hospital. We will attempt to adjust for the correlation among patients seen on the same day using a generalized linear mixed model with a log link and random effect for day, nested within hospital. If convergence problems arise due to small sample sizes, we will collapse by week rather than day. We will also control for hospital as a fixed effect in the model. Results for group comparisons will be presented with odds ratios and 95% confidence intervals.

Secondary outcomes are 45-day post discharge utilization (yes/no), 90-day post discharge utilization (yes/no), QCC defined 30-day readmission (yes/no), and patient centric 30-day readmission (yes/no). Each of the secondary outcomes are dichotomous and will be compared using the same approach as the primary outcome. All tests will be two sided and the data will be analyzed using SAS Enterprise Guide version 6.1. For all outcomes, we assume if there are no visits in the CHS electronic medical record that the value for having a visit is null; therefore, there will be no missing data for the primary or secondary outcome measures.

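### Both 30-day readmission outcomes are compared between arms only among patients admitted after the ED visit, a post-allocation subset that navigation is meant to shrink, and section 6.2 leaves their denominator unclear

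*Combined protocol and SAP*

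**What the plan says.** Section 5.1.2 (items a and b) defines two 30-day readmission outcomes, one for the same facility and one for any facility in the system. Of each it says: "This measure applies to patients that have a hospital admission subsequent the ED encounter". Section 1.3 repeats the restriction; the Protocol Summary omits it. Section 5.1.2 introduces all its outcomes as effects of the navigation pathway compared with usual care.

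The arm is fixed by the day and time of the first telepsychiatric consult (section 5.2). The admit-or-discharge decision comes after that (section 5.3). Section 1.1 hypothesises that navigated patients "will have a lower ED to inpatient conversion than patients who receive usual care", and section 2 says "we expect to decrease the number of patients admitted for inpatient psychiatric treatment".

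Section 6.2 opens with "All analyses will follow intention to treat" and explains this as grouping patients by the allocation of the day of their visit. It adds: "Each of the secondary outcomes are dichotomous and will be compared using the same approach as the primary outcome". For every outcome, the absence of a visit in the system's record is coded null; "therefore, there will be no missing data for the primary or secondary outcome measures".

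On exposure, section 4.4 says: "Patients admitted directly from the ED or have neurocognitive disabilities from the intervention arm will not receive services from the BH-VPN".

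**The concern.** Randomising days makes the two arms comparable as whole groups. It does not make the admitted patients in one arm comparable with the admitted patients in the other if navigation changes who is admitted. Suppose navigation keeps lower-risk patients out of hospital. Those still admitted are then a higher-risk group, and readmission looks worse under navigation with no change in anyone's risk. If it keeps out higher-risk patients, readmission looks better. The plan has no method for this and would report the contrast in the same form as the primary result.

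Part of the subset is also unexposed. Intervention patients admitted directly from the ED get no navigation, so a difference among them is more plausibly selection than effect. Their share is not given.

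The denominator is not settled either. Section 5.1.2 applies the measure to admitted patients only. Section 6.2 can be read as giving every patient a value, so that a never-admitted patient scores no. These are different quantities. Nor does section 5.1.2 give a window for the qualifying admission or refer to the primary outcome's window, of which section 5.1.1 says "Five days were chosen to maximize the conversions attributed to the ED encounter".

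**Working it through.** **The plan's own figure.** Section 6.1 gives 50% vs 35%, 85% power, two-sided α = 0.05 and a total of 414. The two-proportion formula without continuity correction gives [1.96·√(2·0.425·0.575) + 1.036·√(0.25 + 0.2275)]² / 0.15² = 193.5 per arm. With the correction, (193.5/4)·[1 + √(1 + 4/(193.5·0.15))]² = 206.6, so 207 per arm and 414 in total. Then 414 × 1.10 = 455.4, which reproduces the target of 456. With days split equally, that is 228 per arm. The plan gives no figure for the readmission outcomes.

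**Inputs for the illustration.**
- Conversion of 50% vs 35% (section 6.1). These are 5-day rates, used because section 5.1.2 states no window.
- Usual-care readmission of 7% among the admitted. This borrows the system-wide behavioural health rate in section 2, which has no stated 30-day window, and uses it for both outcome versions.
- Assumption: navigation averts admissions and causes none. So 35% of patients are admitted under either arm and 15% only under usual care.
- Assumption: navigation has no effect on readmission itself.

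**Denominators.** 228 × 0.50 = 114 and 228 × 0.35 = 79.8, about 80.

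**Admitted-only rate under navigation.** Let h be the risk in patients still admitted and r the risk of averted patients divided by h. The usual-care rate fixes h:

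0.07 = (0.35h + 0.15rh)/0.50, so h = 0.035/(0.35 + 0.15r).

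The 95% half-width of the difference is 1.96·√(0.07·0.93/114 + h(1−h)/80), ignoring same-day clustering. In all randomised patients, with never-admitted patients scored no, usual care is 0.50 × 0.07 = 3.5% and navigation is 0.35h.

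| r | Admitted-only, navigation (usual care 7.0%) | Shift, points | Half-width, points | All-randomised, navigation (usual care 3.5%) |
|---|---|---|---|---|
| 3 | 4.4% | −2.6 | 6.5 | 1.5% |
| 2 | 5.4% | −1.6 | 6.8 | 1.9% |
| 1.5 | 6.1% | −0.9 | 7.0 | 2.1% |
| 1 | 7.0% | 0 | 7.3 | 2.45% |
| 1/1.5 | 7.8% | +0.8 | 7.5 | 2.7% |
| 1/2 | 8.2% | +1.2 | 7.6 | 2.9% |
| 1/3 | 8.8% | +1.8 | 7.8 | 3.1% |

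In events, the shift runs from −2.1 to +1.4 among 80 patients.

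**Why the denominator matters.** At r = 1/2 the admitted-only reading gives 7.0% vs 8.2% (navigation looks worse), and the all-randomised reading gives 3.5% vs 2.9% (navigation looks better). The usual-care events are the same: 7.98/114 = 7.0% and 7.98/228 = 3.5%.

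**The case against.** Five points can be made for the plan.

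1. A reader might infer that the intention-to-treat sentence contradicts the admitted-only definition. It does not. Section 6.2 uses the term to fix the arm label by allocated day, and admitted patients grouped by allocated day comply. This stands in full.

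2. A reader might see a flat contradiction between section 5.1.2 and the statement that nothing is missing. The documents do not support that either. A patient to whom a measure does not apply is not a missing value, and a specific definition normally governs a general coding rule. What remains is an ambiguity: the coding rule covers all outcomes, and section 6.2 names no admitted-only set.

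3. The subset differs systematically by arm only if navigation changes conversion, which is what the trial tests. This is correct, and the point is conditional on it.

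4. The harm is slight. With no effect on readmission, a two-sided chi-square test on 114 vs 80 gives p < 0.05 in about 5% to 11% of trials across the range of r. The opposite directions at r = 1/2 are differences of 1.2 and 0.6 points, well inside the half-widths. This stands for size. It does not make the contrast a randomised one.

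5. An all-randomised outcome is no cleaner for readmission. Under the same assumptions it reaches p < 0.05 in about 6% to 26% of trials, because fewer index admissions leave fewer readmissions to count. It partly restates the primary outcome. Unrestricted utilisation outcomes already exist, and the same-facility rate is the health system's own measure. This is a good reason not to replace that measure. It is no reason against adding a labelled all-randomised version beside it.

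**Conclusion.** The point holds in a limited form. Both readmission outcomes condition on an event that follows allocation and that navigation is hypothesised to reduce, and the plan would present the resulting contrast as an effect of navigation. The denominator and the qualifying window also need to be stated.

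In the illustration, selection alone moves the navigation rate from 7.0% to between 4.4% and 8.8%, against a half-width of 6.5 to 7.8 points. This rests on the planning conversion rates being met over an unstated window, on the borrowed 7%, on assumed risk ratios of 3 to 1/3, and on navigation only averting admissions. A different window would change both denominators.

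Two further readings go too far. The admitted subset is not wholly unexposed: a patient discharged with navigation and admitted later belongs to it. And the trial's main result is not in question: the primary analysis and the sample size do not depend on these two secondary outcomes. The change should still be made before analysis, so that the denominator is not chosen with results in view.

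**What to change.** - State one denominator for each readmission outcome, worded the same way in sections 1.3, 5.1.2 and 6.2, and say whether never-admitted patients are excluded or scored no.
- State the window that makes an admission the index admission, for example the 5-day window of section 5.1.1.
- Keep the system-defined admitted-only rates by arm. Label them non-randomised and descriptive, with no causal claim.
- Add an all-randomised outcome beside them: an index admission followed by readmission within 30 days, never-admitted patients scored no, analysed by allocated day, in same-facility and any-facility versions.
- Label this added outcome a total effect that must not be read as lower readmission risk per admission.

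The cost is wording and a little programming on data already to be extracted; no new data are needed. The drawback is that the added outcome falls when admissions fall: at equal per-admission risk it is 3.5% vs 2.45%, a relative fall of 1 − 2.45/3.5 = 30%. It is also imprecise, with a 95% half-width of about 3 points. The question of readmission risk per admission stays descriptive.

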**Protocol Approved By:**

PRINCIPAL INVESTIGATOR:

EXECUTIVE SPONSORS:

\_\_\_\_\_  
[name]

\_\_\_\_\_  
Print Name

\_\_\_\_\_  
Date

\_\_\_\_\_  
Signature

\_\_\_\_\_  
Print Name

\_\_\_\_\_  
Signature

PROTOCOL SUMMARY	
Study Title	HIIN – BH: An evaluation of Emergency Department to admission conversion among patients with a telepsychiatric consult who are followed by a behavioral health - virtual patient navigation team
Study Design	A randomized, quality improvement evaluation
Study Objectives	
The primary objective is to evaluate the effect of a behavioral health virtual navigation team compared to usual care among patients with a telepsychiatric consult, on Emergency Department to inpatient conversion.
 
Secondary objectives of the evaluation include: Compare the following between the intervention group and the usual care group:
 
 
○ 45-day post discharge utilization (ED, inpatient, and observation encounters)
 
○ 90-day post discharge utilization (ED, inpatient, and observation encounters)
 
○ CHS Quality, Comfort, and Care defined 30-day readmission rate. This is a readmission rate among patients with an inpatient readmission to the same CHS facility as the index encounter.
 
○ The patient-centric defined 30-day readmission rate. This is a readmission rate among patients with an inpatient or observation readmission to any CHS facility.
 
 
Additional analyses will be to explore:
 
 
a. As a sub-analysis, qualitative outcomes will be collected and measured with patients, providers, and leaders. These outcomes will be collected and evaluated, per a sub-study protocol addendum.
 
b. Historical health records may be pulled to explore baseline rates of risk factors among prior behavioral health patients at CHS.
 

Inclusion/ Exclusion Criteria	
Inclusion:
 
 
● 18 years of age or older
 
● ED visit
 
● Completed telepsychiatric consult at the ED visit
 
● Telepsychiatric consult occurs Monday through Friday during the Navigator’s potential hours of operation
 

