### **1.3. Secondary Objectives**

The secondary objectives are to examine the behavioral health – virtual patient navigation team’s effect on additional patient outcomes, such as the

- i. CHS Quality, Comfort, and Care 30-day readmission rate. This is a readmission rate among patients with an inpatient readmission to the same CHS facility as the index encounter. This measure applies to patients that have a hospital admission subsequent the ED encounter.
- ii. The patient-centric 30-day readmission rate. This is a readmission rate among patients with an inpatient or observation readmission to any CHS facility. This measure applies to patients that have a hospital admission subsequent the ED encounter.
- iii. 45-day post ED discharge utilization (ED, inpatient, observation encounters)
- iv. 90-day post ED discharge utilization (ED, inpatient, observation encounters)

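### The 45- and 90-day utilization outcomes do not exclude the admission arising directly from the index ED visit, so every primary event also counts as utilization

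*Combined protocol and SAP*

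**What the plan says.** - **Utilization.** Section 5.1.2 lists "45-day post ED discharge utilization. Utilization is defined as an inpatient, observation, or ED encounter at a CHS facility" and "90-day post ED discharge utilization. Utilization is defined as an inpatient, observation, or ED encounter at a CHS facility". Section 1.3 names the same start point, ED discharge.
- **Primary outcome.** Section 5.1.1 counts patients who "within 5 days of their ED discharge are admitted for any reason to a CHS facility as an inpatient or observation patient". It adds: "In the electronic medical record, 2 hospital encounters are shown, the ED encounter and the inpatient\observation hospital encounter".
- **Analysis.** Section 6.2 reads "Secondary outcomes are 45-day post discharge utilization (yes/no), 90-day post discharge utilization (yes/no" and analyses these outcomes in the same way as the primary. Here, and in the Protocol Summary, the discharge is not tied to the ED.
- **Population.** Section 4.4 assesses all eligible patients in both arms by intention to treat, including those admitted. It also says that intervention-arm patients admitted directly from the ED receive no navigation.
- **Readmission outcomes.** Sections 1.3 and 5.1.2 restrict the two 30-day readmission rates to patients who had a hospital admission after the ED encounter.

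No section says that the admission belonging to the index visit is left out of utilization, and none says outright that it is included.

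**The concern.** The primary and the utilization outcomes share a start point. The utilization event types include those of the primary, and a 5-day window lies inside 45 and 90 days. A literal extract would therefore score every conversion as post-discharge utilization.

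This matters because the programme is meant to send more patients home, and the natural follow-on question is whether they then return. The 30-day readmission rates cannot answer it, since they exclude patients who were never admitted. The two utilization outcomes are the only listed secondary outcomes that cover patients who went home. As worded, a fall in index admissions alone lowers them, and a rise in returns among the additional discharged patients could be offset and go unseen.

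**Working it through.** **The plan's own figure.** Section 6.1 assumes 50% in usual care and a 15-point absolute reduction (so 35%), 85% power, α = 0.05 and a total of 414. The two-proportion formula with continuity correction gives 207 per arm, 414 in total, which matches. Without the correction it gives 388. Inflating by 10%, 207 × 1.10 = 227.7, rounded up to 228 per arm, or 456, which also matches. So 50% and 35% are the plan's design rates.

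**Inputs**
- c, conversion: 50% usual care, 35% BH-VPN (section 6.1).
- u, the chance of any new CHS encounter in the window other than a primary conversion: not in the documents. Assumed equal in both arms and in converters and non-converters; shown for 20% to 40%.
- s, the share of conversions that are direct admissions from the index ED visit: not in the documents. Assumed equal in both arms; s = 1 is the upper limit.

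**Formulas**
- As defined now: c + (1 − c) × u.
- With the direct index stay left out: u + (1 − s) × c × (1 − u). Conversions after the patient has left the ED still count.
- Arm difference as defined now: (1 − u) × 15 points. With the direct stay left out: (1 − s) × (1 − u) × 15 points.
- Artefact, the gap between these two: s × (1 − u) × 15 points.

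**Results**

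| u | Usual care, as defined | BH-VPN, as defined | Difference | Odds ratio | Artefact if s = 1 | Artefact if s = 0.5 |
|---|---|---|---|---|---|---|
| 20% | 60.0% | 48.0% | 12.0 | 0.615 | 12.0 | 6.0 |
| 30% | 65.0% | 54.5% | 10.5 | 0.645 | 10.5 | 5.25 |
| 40% | 70.0% | 61.0% | 9.0 | 0.670 | 9.0 | 4.5 |

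Example for u = 30%: 0.50 + 0.50 × 0.30 = 0.65, and 0.35 + 0.65 × 0.30 = 0.545.

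If s = 1 and navigation has no effect on returns, the chance of a significant utilization benefit at 207 per arm (the size before the 10% inflation) is about 69%, 59% and 49% for u = 20%, 30% and 40%. The same calculation, without continuity correction, gives 87% for the primary comparison.

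**Could a rise in returns be hidden?** Take s = 1, with returns among non-converters of 30% in usual care and 40% under BH-VPN. The present measure gives 65% against 0.35 + 0.65 × 0.40 = 61%, still in favour of navigation. With the direct stay left out, and later use after direct admission assumed to be 30% in both arms, it gives 30% against 0.35 × 0.30 + 0.65 × 0.40 = 36.5%, against navigation. The present measure would show no difference only at (0.65 − 0.35) / 0.65 = 46% returns under BH-VPN.

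**The case against.** **The start point is not settled.** The Protocol Summary and section 6.2 omit the ED, and section 4.4 lists discharge from the ED as a disposition distinct from admission. If the clock started at hospital discharge for admitted patients, most of the overlap would go. This shows that the wording must be reconciled, but it does not remove the problem. The outcome definitions in sections 1.3 and 5.1.2 name ED discharge, section 5.1.1 uses that term for patients who convert, and the looser wording does not override them.

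**The definition matches the stated objective.** This stands. A reader might infer that the protocol promises a measure of use after the index episode; no section says so. Total CHS use after the ED visit is a coherent outcome for a programme that aims to reduce admissions. What it cannot do is stand in for return visits.

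**Not every conversion is an artefact.** This also stands. A reader might infer that half of usual-care patients score yes before any return is possible. The 5-day window in section 5.1.1 can include patients who left and came back, which is genuine utilization, and the documents do not give the split. In addition, the 50% in section 6.1 is an inpatient rate counted from ED presentation, not quite the section 5.1.1 measure.

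**Moving the clock has a price.** Restarting at hospital discharge makes time zero depend on disposition, which the intervention aims to change. ED discharge gives everyone one start point and matches the 45-day navigation period. The fix below therefore keeps it.

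**Conclusion.** The point holds on the definitions as written: every primary event is also a yes on both utilization outcomes, and no section excludes it. The overlap does not depend on u or s; only its size does. At the plan's 50% versus 35%, the artefactual benefit is s × (1 − u) × 15 points. For u of 20% to 40% it is at most 12 to 9 points, reached only if all conversions are direct admissions, and it shrinks in proportion as s falls. These figures assume that u and s are the same in both arms and that u is the same in converters and non-converters.

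A reader might go further and infer that the trial's main result is compromised. The documents do not support that. The only stated hypothesis concerns conversion, and the primary endpoint, the sample size and the allocation are unaffected. This is an inexpensive improvement to two secondary outcomes.

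**What to change.** In sections 1.3, 5.1.2 and 6.2, and to match in the Protocol Summary:

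1. State one start point, ED discharge, for all allocated patients in both arms.
2. Do not count an inpatient or observation stay entered directly from the index ED visit.
3. Count any new ED, inpatient or observation encounter after that, including an admission after the patient has left the ED.
4. Report the present definition alongside, labelled *total utilization including index admission*.
5. As a sensitivity analysis, start the clock at hospital discharge for directly admitted patients.

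Settle the wording before results are known.

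The cost is the wording and one encounter-linkage step in the record extract. Trial conduct does not change. The drawback is that directly admitted patients have somewhat less time at risk within the fixed window. If navigation lowers direct admissions, usual care would have more such patients, which tilts the comparison slightly against navigation. The size depends on length of stay, which the documents do not give. Item 5 checks this, at the price of a start point that depends on disposition.
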